12.2 Endpoints

12.2.1 Efficacy

The objective response rate will be estimated for each tumor histology type evaluated. The estimate of the objective response rate will be calculated based on the maximum likelihood estimator (i.e., crude proportion of subjects whose best overall response is Complete Response (CR) or PR. The estimate of the objective response rate will be accompanied by 2-sided 95% exact binomial confidence intervals.

The duration of objective response will be calculated for subjects who achieve CR or PR. For such subjects, the duration of objective response is defined as the number of days from the start date of PR or CR (whichever response is achieved first) to the first date that progressive disease is objectively documented. Disease progression will be determined by the Investigator using RECIST (version 1.1). The duration of objective response will be right-censored for subjects who achieve CR or PR and meet 1 of the following conditions: 1) non-protocol anticancer treatment started before documentation of disease progression, 2) death or documented disease progression after more than 1 missed disease assessment visit, or 3) alive and does not have documentation of disease progression before a data analysis cutoff date.

The duration of objective response will be summarized descriptively using the Kaplan-Meier method. The 50th percentile of the Kaplan-Meier distribution will be used to estimate the median response duration.

Progression free survival will be defined as the time (in months) from enrollment to either first observation of progressive disease or occurrence of death due to any cause within 126 days (approximately 2 time intervals for tumor assessments) of either first administration of tipifarnib or the last tumor assessment. In subjects without a progression date or with a death date more than 126 days after the first administration of study drugs or the last tumor assessment, the PFS time should be censored on the date of last tumor assessment or date of first administration of study tipifarnib. Progression free survival analyses should consider tumor assessments after treatment discontinuation or metastatic surgery. Sensitivity analyses for PFS will be performed according to the FDA Guidance for Industry Clinical Trial Endpoints for the Approval of Cancer Drugs and Biologics (May 2007).

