9.2. Exploratory Efficacy Analyses

The duration of objective response (DOR) will be calculated for subjects who achieve CR or PR. For such subjects, the DOR is defined as the number of days from the start date of PR or CR (whichever response is achieved first) to the first date that progressive disease is objectively documented. Disease progression will be determined by the Investigator using RECIST (version 1.1). The DOR will be right-censored at the date for subjects who achieve CR or PR and meet 1 of the following conditions: 1) when non-protocol anticancer treatment started before documentation of disease progression, 2) when death prior to documented disease progression or documented disease progression after more than 1 missed disease assessment visit, or 3) when alive and does not have documentation of disease progression before a data analysis cutoff date. (Therefore, analysis cutoff date will be used as the censoring date).

Progression free survival (PFS) will be defined as the time (in months) from first dose (Cycle 1 Day 1) to either first observation of progressive disease or occurrence of death due to any cause within 126 days (approximately 2 time intervals for tumor assessments) of either first administration of tipifarnib or the last tumor assessment. Observation of progressive disease can be by either documented radiographic progression (i.e., scan results) or documentation of symptomatic or clinical progression agreed upon and documented by investigators. In subjects without a progression date or with a death date more than 126 days after the first administration of study drugs or the last tumor assessment, the PFS time should be censored on the date of last tumor assessment or date of first administration of study tipifarnib. PFS analyses should consider tumor assessments after treatment discontinuation or metastatic surgery.

The DOR and PFS, will be summarized descriptively using the Kaplan-Meier (KM) method. The 25th, 50th, and 75th percentiles of the Kaplan-Meier distribution will be used to describe the median response duration and median PFS.

The median DOR and PFS and corresponding pointwise 95% confidence interval will be displayed by cohort for the FAS population and for the PP population, and for the subgroups.

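### SAP 9.2 leaves the DOR censoring date unstated for progression found after more than one missed scan; either available reading credits the unscanned gap as response, while PFS counts the same progression as an event

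*SAP*

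**What the plan says.** SAP 9.2 runs DOR from first response "to the first date that progressive disease is objectively documented". It then says: "The DOR will be right-censored at the date for subjects who achieve CR or PR and meet 1 of the following conditions". The sentence gives no date at that point and goes on to three conditions:

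1. New anticancer treatment begins before progression is documented.
2. "when death prior to documented disease progression or documented disease progression after more than 1 missed disease assessment visit".
3. The subject is alive without progression at the data cutoff.

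Only after the third does a date appear: "Therefore, analysis cutoff date will be used as the censoring date".

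Protocol 12.2.1 has the same progression limb, "death or documented disease progression after more than 1 missed disease assessment visit", and names no censoring date for any DOR condition.

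The PFS event, also in SAP 9.2, is "either first observation of progressive disease or occurrence of death due to any cause within 126 days" of first dose or the last tumor assessment. PFS is censored only in subjects with no progression date or with a late death. The censoring date is then the last tumor assessment or the first dose. There is no missed-scan rule for progression.

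**The concern.** Censoring at a given date says that the subject was known to be event-free up to that date. After more than one missed scan this is not known, and the scan that ends the gap shows that the response was lost at some point within it. If the censoring date falls at or after that scan, the responder stays in the risk set for the whole gap and then leaves without an event. The error has one direction: it raises the DOR curve.

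The same scan would be an event for PFS and a censoring for DOR. SAP 9.2 lists censoring status and progression date per subject for both endpoints, so the disagreement would be visible in the outputs. The first condition has the same gap in wording. Read the same way, a responder who starts new therapy is followed to the start of that therapy and not to the last scan before it.

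DOR medians and curves are to be shown by cohort, population and subgroup. Planned cohorts are 18, 37 and 20 evaluable subjects, so responders will be few and one or two such cases can change a curve.

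**Working it through.** Neither document gives a missed-scan rate, an event count or a precision target for DOR, so there is no plan figure to reproduce. Rates and curve shapes below are assumptions.

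**Which date?** Three candidates:
- Progression date: follows if the date is taken to be the day on which the listed condition occurs. This is the natural reading, but it is not stated.
- Analysis cutoff: follows only if the parenthesis after the third condition covers all three. It cannot precede the progression in the analysis, so it credits at least as much event-free time.
- Last adequate assessment: not named for DOR anywhere in SAP 9.2.

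**Length of the gap.** Scans are due at about weeks 8, 16, 24, 36, 48, 60 and so on (SAP 4.1). Two are missed and progression is found at the next scheduled scan:

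| Last scan | Missed | Progression | Gap |
|---|---|---|---|
| week 8 | 16, 24 | 36 | 28 weeks = 196 days = 6.4 months |
| week 16 | 24, 36 | 48 | 32 weeks = 224 days = 7.4 months |
| week 24 | 36, 48 | 60 | 36 weeks = 252 days = 8.3 months |

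Months are days / 30.4375 (SAP 7.1). Later starting points also give 36 weeks. If the response is itself confirmed at a scheduled scan, the gap starts at week 16 or later.

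**One subject.** Day 22 of Cycles 2, 4, 6, 9 and 12 falls on days 50, 106, 162, 246 and 330. Take PR at day 50, last scan at day 106, days 162 and 246 missed, and progression at day 330.
- DOR censored on the progression date: 330 − 50 = 280 days.
- DOR censored at the last scan: 106 − 50 = 56 days.
- PFS: event at the day-330 scan.

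**A small cohort (assumed).** Twelve responders: two progress at each of 8, 16, 28 and 40 weeks of response, one at 52 weeks, and one is censored at 64. The remaining two have progression at 40 weeks after two missed scans, with their last scan at 8 weeks. Kaplan-Meier at 40 weeks:
- Late progression as event: 0.500 × (1 − 4/6) = 0.167
- Censored on the progression date: 0.500 × (1 − 2/6) = 0.333
- Censored at the last scan: (10/12)(6/8)(4/6)(2/4) = 0.208

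Taking the median as the first time the curve reaches 0.5, it is 28 weeks under all three rules. With three affected of thirteen, the medians are 40 (event), 40 (progression date) and 28 weeks (last scan).

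**A range of rates (assumed).** Simulation of 60,000 responders: response at day 50, exponential DOR with median 6 months (182.6 days), scans on the schedule above. A fraction f miss the scan that would have detected progression and the next one. The confirmation requirement is ignored. DOR rate at 12 months:

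| f | Full scanning | Censored on progression date | Censored at last scan | Late progression as event |
|---|---|---|---|---|
| 5% | 25.1% | 28.2% | 26.7% | 26.3% |
| 10% | 25.2% | 31.7% | 28.5% | 27.5% |
| 20% | 25.0% | 38.0% | 31.9% | 29.4% |

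Hand check. The last scan within 12 months of response is day 414, which is 364 days after it: 2^(−364/182.6) = 0.2512, matching full scanning. An affected subject is found by day 414 only if true progression came by day 246, 196 days after response; 2^(−196/182.6) = 0.4753 have not progressed by then. Late progression as event is therefore (1 − f) × 0.2512 + f × 0.4753 = 0.262, 0.274 and 0.296, which agrees with the last column within simulation error.

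At f = 20% the median is 280 days under all three rules. If the missed scans are instead the detecting one and the one before it, the progression-date figure at 20% is 34%, not 38%.

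**The case against.** **The SAP does not say that censoring is on the progression date.** This stands. A reader might take that as the stated rule, but it is an inference from an unfinished phrase. What the documents support is that the date is unstated and that neither available reading gives the last adequate scan.

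**The gap has no fixed minimum.** This also stands. A reader might infer at least three 8-week intervals, or 24 weeks. At scheduled scans the shortest gap is 28 weeks, because three consecutive 8-week intervals would have to start at baseline, before any response. Unscheduled scans are allowed, so progression can also be found sooner after the second missed visit. An assumed extra confirmation scan at week 12 would give 24 weeks.

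**The 12-month rate is not a planned statistic.** Correct. SAP 9.2 plans quartiles, the median with its confidence interval, and curves. The rate measures the upward shift in a displayed curve, and the median often does not distinguish the rules.

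**Imaging is fixed regardless of dosing delays, so long gaps may be rare.** Possible; at 5% affected the rules differ by about two percentage points.

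**Last-scan censoring is not the closest rule to full scanning.** True under these assumptions: at 20% affected it gives 32%, against 29% when late progression is an event and 25% with full scanning. The second analysis is therefore needed.

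**The 126-day limit might be read as covering progression as well as death, which would bring PFS into line with DOR.** This fails, because the PFS censoring sentence applies the limit only to deaths.

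**Conclusion.** The point holds as a defect of wording with a one-directional consequence. SAP 9.2 does not state where DOR is censored when progression follows more than one missed visit. Both readings open to a programmer credit the gap (28 to 36 weeks at scheduled scans) as event-free response. PFS counts the same progression as an event, and no planned DOR sensitivity analysis varies the missed-visit rule.

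The size depends on an unknown rate. For 5% to 20% of responders affected, with exponential DOR, a 6-month median and the missed-scan pattern assumed above, the progression-date reading lifts the 12-month DOR from 25% to between 28% and 38%.

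A reader might infer that the trial's main result or the median DOR is inflated. The documents do not support that. DOR is exploratory and descriptive, the ORR rule counts responses and uses no duration, and the median was often the same under every rule compared. The SAP should be corrected, but the trial's primary conclusion does not depend on it.

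**What to change.** In SAP 9.2, state one censoring date for each DOR condition:
- Progression after more than one missed visit: the last adequate tumor assessment before the missed visits. This keeps the protocol's decision to censor these subjects and changes only the date.
- New anticancer therapy: the last tumor assessment before it starts.
- Death before progression, which shares the second condition, and no progression at cutoff: each with its own explicit date, so that the cutoff parenthesis cannot be read as covering everything.

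Report alongside this an analysis that counts the late progression as a DOR event on its date, as PFS does. Do not add a missed-scan censoring rule to PFS: that would turn documented progressions into censored observations.

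The cost is SAP wording, one extra derived date and one extra run, with no new data. Reported DOR may be shorter.

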Tumor assessments will be performed at screening and approximately every 8 weeks starting at the end of cycle 2 for the first 6 months (Cycles 2, 4, 6) and then every 12 weeks (Cycles 9, 12, 15, etc.), or sooner if deemed necessary by the Investigator, and will continue until disease progression. A tumor assessment will be performed upon treatment discontinuation (End of Treatment visit) if the reason for discontinuation is other than disease progression and no tumor assessment was performed in the prior 8 weeks, or a tumor assessment is required for the confirmation of response to treatment. Subjects who discontinue treatment for reasons other than disease progression must continue tumor assessments until disease progression, withdrawal of subject's consent or initiation of another anticancer therapy. Determination of objective tumor response will be performed by the Investigator. However, tumor images may be de-identified of subject's personal information at the clinical sites and collected by the Sponsor or designee to undergo an external independent radiological review if the sponsor deems it necessary for the final assessment of the efficacy of the treatment. If an independent radiological review were to be conducted, reviewers would be blinded to Investigator's tumor response assessments. An independent review committee charter would be generated to provide the specific procedures that would be filed with Institutional Review Board (IRB) and regulatory authorities.

Subjects with a solitary site of disease who have experienced a response may be considered for surgical resection. Subjects with a Partial Response (PR) and residual disease after salvage surgery are eligible to continue on study therapy.

Upon disease progression, all subjects in the study cohort will be followed approximately every 12 weeks for survival and the use of subsequent therapy until either death or 12 months after accrual in the subject's study cohort has been completed, whichever occurs first. Information on survival and subsequent anticancer therapy may be collected by phone.

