7.6. Handling of Dropouts or Missing Data

Where individual data points are missing because of insufficient samples, dropouts, or other reasons, the data will be analyzed based on reduced denominators. For survival analysis, dropouts without confirming events will be treated as censored.

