The KM curves of DOR and PFS by each cohort will be displayed for the FAS population, the PP Population, and for the subgroups in figures. A per subject summary of DOR, such as treatment initiation date, progression date, first response date, durations, censoring status, best overall response, and analysis population inclusion, will be provided. Similarly, a per subject summary of PFS, including enrollment date, treatment initiation date, progression date, duration, censoring status, best overall response, and analysis population inclusion, will also be provided.

Subgroup analysis may be conducted to estimate PFS and DOR in the subset of subjects with partial response. Sensitivity analysis may be conducted to assess the impact of the median survival estimation method. Interpolation based estimates can be used to estimate the median

Protocol KO-TIP-001

survival whenever the sample size is small or there is not sufficient information (events) to robustly estimate the median survival based on KM function.

Further analysis may include the comparison of the PFS between tipifarnib and prior therapies. A *P* value comparing the two PFS profiles (prior therapy and the current using tipifarnib) will be obtained using Wei-Lin (Cox regression based) robust estimator.

If biomarkers including somatic mutations in archival tumor tissue have been successfully obtained for enough subjects, the relationship of the detection of tissue biomarkers potentially related to tipifarnib activity will be investigated as described in the protocol.

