9.3. Other Efficacy Analyses

Per subject data on detail of tumor burden marker, and on subsequent therapy and survival status will be displayed in listings.

Waterfall figures and spider plots will illustrate best overall percent change in tumor burden (defined as sum of diameters) for the FAS population, the PP population and by subgroup.

An analysis of overall survival to estimate median overall survival time and corresponding 95% confidence interval and provide per subject summary of overall survival will be conducted. Overall survival will be defined as the time (in months) from first dose (Cycle 1 Day 1) to the occurrence of death due to any cause. In subjects without a death date, the OS will be censored on 1) the last date of survival status if alive, 2) a data analysis cutoff date for subjects with no survival status documentation, or 3) the date a subject withdraws consent or is lost to follow-up, if there is no additional information.

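### Responders alive without documented progression have DOR censored at the analysis cutoff, not at the last scan as PFS is, so unscanned time counts as continued response

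*SAP*

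**What the plan says.** SAP section 9.2 defines the DOR event as the first objectively documented progression. It lists three reasons for right-censoring a responder: (1) new anticancer treatment before progression; (2) death before progression, or progression found after more than one missed assessment; (3) alive with no documented progression before the data cutoff. For the third it adds that the "analysis cutoff date will be used as the censoring date".

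The PFS paragraph of the same section uses another date: for subjects without a progression date, "the PFS time should be censored on the date of last tumor assessment" (or on the date of first dose).

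Four other passages matter.

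- SAP 4.1: subjects who stop treatment for reasons other than progression "must continue tumor assessments until disease progression, withdrawal of subject's consent or initiation of another anticancer therapy".
- SAP 7.6: in survival analyses, "dropouts without confirming events will be treated as censored". No date is given.
- SAP 9.3: overall survival (OS) is censored at "the last date of survival status if alive", at the cutoff where there is no survival documentation, or at "the date a subject withdraws consent or is lost to follow-up" if nothing further is known.
- Protocol 12.2.1: the same three DOR conditions, with no censoring date. The cutoff date is therefore a SAP addition, and SAP section 14 does not list it as a change.

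**The concern.** Progression can be documented only while the tumor is being assessed. Under condition 3, a responder whose scans have stopped keeps accruing event-free DOR time until the cutoff with no tumor data behind it. The same subject then has two last-observed dates in one SAP section, and DOR can run past that subject's PFS censoring date. Depending on which OS rule applies, it can run past the OS censoring date as well.

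The plan leaves a route to this. By SAP 4.1, scanning after treatment ends at progression, new therapy or consent withdrawal. Progression is the DOR event and new therapy is condition 1. Withdrawal has no DOR rule of its own, so condition 3 is the only one left for a responder who is alive. Condition 2 already treats a progression found after a long gap in scanning as unreliable; a responder who never returns from such a gap is credited with all of it.

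What is at stake is the planned DOR display: "The KM curves of DOR and PFS by each cohort will be displayed", and also by subgroup. Responders will be few in each, so one long unscanned tail can be visible.

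**Working it through.** The plan states no DOR figure to reproduce, so the check has three parts: direction, a single-subject example, and size.

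**Direction.** The Kaplan-Meier estimate is the product over event times of (1 − d/r), where d is the number of events and r the number still at risk. Moving a censoring date from last scan to cutoff leaves every d unchanged and can only raise r. Each factor, and so the curve, is equal or higher.

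**Single-subject example.** The scan days are the protocol's; the withdrawal and cutoff dates are assumed.

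- Response at Cycle 2 Day 22: 28 + 22 = study day 50.
- Confirmed at the last scan, Cycle 4 Day 22: 84 + 22 = study day 106.
- Consent withdrawn on day 120, nothing known afterwards; cutoff on day 730 (24 months).
- PFS is censored at day 106. OS is censored at day 120 under the withdrawal rule.
- DOR to the last scan: 106 − 50 = 56 days; 56/30.4375 = 1.8 months.
- DOR if condition 3 is applied: 730 − 50 = 680 days; 680/30.4375 = 22.3 months.

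**Size.** The measure is the height of the Kaplan-Meier DOR curve at 12 months under cutoff censoring minus its height under last-scan censoring. From the documents: scans on Day 22 of Cycles 2, 4, 6, 9, 12 and so on. Assumed:

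- response first seen at scan 1 or 2;
- exponential DOR with true median 6 months;
- cutoff uniform 6 to 36 months after response;
- loss from scanning uniform over the 12 months after response;
- deaths after loss dated at the last scan under both rules.

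There were 3,000 to 4,000 simulated trials per setting (Monte Carlo standard error at most 0.0015). Ranges run across 7, 8, 15 and 16 responders.

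| Responders lost to scanning | All lost alive at cutoff | Median survival after loss 24 months | 12 months | 8 months |
|---|---|---|---|---|
| 5% | +0.023 | – | – | +0.010 |
| 10% | +0.040 to +0.042 | +0.026 to +0.028 | +0.019 to +0.020 | +0.014 to +0.016 |
| 20% | +0.071 to +0.078 | +0.047 to +0.051 | +0.032 to +0.036 | +0.024 to +0.026 |

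With no loss the difference is +0.005 to +0.006. It was never negative in any trial. At 20% lost, only 12–13%, 8%, 6% and 4% of responders (left to right) actually reach condition 3 unscanned, because the others progress or die first.

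With a true median DOR of 12 months:

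- 10% lost: from +0.030 to +0.031 (all alive) down to +0.013 (8-month survival);
- 20% lost: from +0.056 to +0.058 down to +0.019 to +0.021.

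A second simulation used a constant monthly loss and no deaths (15 responders, response at week 8, cutoff 12 to 36 months after first dose). With a true median of 9 months the 12-month rates, cutoff versus last scan, were:

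- no loss: 0.397 and 0.397, no difference;
- 2% per month: 0.464 and 0.393, difference +0.071;
- 5% per month: 0.553 and 0.400, difference +0.153.

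Over true medians of 6 to 14 months and loss of 2% to 5% per month, the difference was about +0.05 to +0.18.

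**The case against.** **The example subject may not meet condition 3.** That condition requires the subject to be alive. After withdrawal with no later information, vital status at cutoff is unknown, and SAP 4.1 starts survival follow-up only at progression. This stands as a reading, and it is why the 680-day figure is conditional. But if condition 3 does not apply, no DOR rule does, and SAP 7.6 supplies no date. The sentence needs mending either way.

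**The OS contrast is limited.** A subject confirmed alive near cutoff has a late OS date too, and OS itself uses the cutoff when there is no survival documentation. Both points are correct. The argument rests on the PFS contrast, which is unconditional, and no OS change is asked for.

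**The SAP does not plan a 12-month DOR rate.** It plans quartiles and a median with a confidence interval, and with moderate loss the median often does not move. Under a 6-month true median it was identical under both rules in 92–99% of trials with 8 responders. With 15 responders it was identical in 64% (20% lost, all alive) to 98% (no loss). The result depends on the assumptions: in the second simulation, 2% monthly loss moved the typical median from 9.2 to 12.0 months. No particular percentile shift is claimed here; the 12-month rate measures the height of a curve that will be displayed.

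**The wording on conditions 1 and 2, "right-censored at the date for subjects who achieve CR or PR", could mean the date on which each condition occurs.** That is possible, but a programmer should not have to infer it. Dating deaths at death in the simulation changes the results by about 0.003 or less.

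**The effect is exploratory, of unknown size, and partly visible in the per-subject listings.** All true. Scans after discontinuation are mandatory, so the route is narrow. These points limit the importance of the rule but do not defend its date.

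**Conclusion.** The concern holds. The SAP states a censoring date that credits unscanned time as event-free response, against its own PFS convention a paragraph later. The direction is certain: the DOR curve can only be equal or higher.

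The size is not fixed by the documents. It is negligible with scanning on schedule. In the main simulation, with a true median DOR of 6 months, it is roughly +0.01 to +0.08 on the 12-month DOR rate when 5% to 20% of responders stop being scanned. It is larger under sustained monthly loss without deaths. These figures rest on assumed loss rates, survival after loss, DOR distribution and cutoff timing, and the true loss may be zero. DOR is exploratory and descriptive, and neither the primary ORR analysis nor the two-stage decision is touched. The change should be made because the rule is systematically favourable, responders are few, no planned sensitivity analysis tests the censoring date, and correction is nearly free.

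**What to change.** In SAP 9.2, DOR condition 3, replace the cutoff with the date of the last tumor assessment on or before the analysis cutoff, matching PFS. If only adequate or evaluable assessments are to count, define the term. Add a clause that responders who withdraw consent or are lost to follow-up without documented progression follow the same rule.

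In the same edit, name the censoring date for conditions 1 and 2, and record the DOR censoring dates in SAP section 14, since the protocol gives none. Whether death should be censored in DOR at all is a separate question.

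The cost is one parenthesis and one clause, plus the tidying of conditions 1 and 2. The dates for condition 3 come from scans already collected. DOR follow-up becomes slightly shorter and the DOR curve possibly less favourable; ORR does not change.
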